## ABSTRACT

**Introduction:** The endogenous production of nitric oxide (NO) is reduced in autosomal dominant polycystic kidney disease (ADPKD) and may contribute to early-onset hypertension, which is present in 60% of patients. Beetroot juice (BRJ) is a natural dietary source of nitrate and reduces blood pressure in other study populations. The aim of this study is to evaluate the efficacy of BRJ on reducing blood pressure in hypertensive adults with ADPKD.

**Methods and analysis:** ADPKD patients with hypertension (n=60) will be randomised (1:1) to receive either nitrate-rich or nitrate-depleted (placebo) BRJ using a randomised, double-blind, placebo-controlled study design. The effect of BRJ on blood pressure will be assessed over a 4-week study period. The co-primary endpoints are a change from baseline in mean automated clinic systolic and diastolic blood pressure. Secondary endpoints are changes in daily home blood pressure, changes in albuminuria, NO metabolites (plasma nitrate and nitrite), plasma asymmetric dimethylarginine (ADMA) levels (a naturally occurring endogenous inhibitor of NO increased in ADPKD), and adverse events.

**Ethics and dissemination:** Approval was obtained from the Western Sydney Local Health District (WSLHD) Human Research Ethics Committee (HREC). The results of this study will be disseminated at national and international Scientific Meetings and submitted for publication in peer-reviewed international journals.

**Trial registration:** NCT05401409 (clinicaltrials.gov; National Library of Medicine)

## Summary

|                       |  |
|-----------------------|--|
| Study Title           | Double-Blind, Randomised Placebo-Controlled Study to Determine the Effect of Beetroot Juice on Reducing Blood Pressure in Hypertensive Adults with Autosomal Dominant Polycystic Kidney Disease (BEET-PKD Study)   |
| Rationale             | Autosomal dominant polycystic kidney disease is the most common genetic cause of kidney failure. Previous studies have shown that the endogenous production of nitric oxide is reduced in ADPKD and this may lead to early-onset hypertension, which is present in 60% of patients. Beetroot juice (BRJ) is natural dietary source of oral nitrate and reduces blood pressure and improves exercise performance in other populations but its role in ADPKD is unknown. The aim of this study is to evaluate the efficacy and safety of BRJ in reducing blood pressure in adults with ADPKD.  |
| Primary Objective     | Determine the efficacy of daily consumption of BRJ (400 mg nitrate) on decreasing clinic systolic and diastolic blood pressure in ADPKD participants with hypertension over 4 weeks.   |
| Secondary Objectives  | 
 
Determine the effect of BRJ on decreasing home systolic and diastolic blood pressure readings
 
Determine the effect of BRJ on reducing albuminuria
 
Determine the effect of BRJ on increasing NO metabolites (plasma/urine), and reducing asymmetric dimethylarginine (plasma) levels
 
  |
| Exploratory Objective | 
 
Characterisation of the baseline oral microbiome in ADPKD using salivary bacterial genomic data
 
Determine the effect of 4 weeks of BRJ consumption on the oral microbiome in ADPKD patients
 
Measure the effect of BRJ on urinary the development of urinary N-nitroso compounds
 
   |
| Study Design          | This is a randomised, double blind placebo-controlled trial. Participants with treated hypertension (defined as being on at least one anti-hypertensive medication; n=60) will be included in the study. The total duration of the study is 5 weeks. There will be a 7 day run-in period where participants will be asked to record BP daily to determine adherence and baseline blood pressures. Participants will then be randomised (1:1) to receive an oral daily dose of either BRJ (400mg nitrate) or nitrate-depleted BRJ for 28 days. Blood pressure will be measured in clinical and at home using a standard and validated automated oscillometric blood pressure (AOBP) device provided to all participants. Blood, urine and saliva samples will be collected before and after the intervention. |
| Primary Endpoint      | Reduction in mean automated clinic systolic and diastolic blood pressure relative to baseline  |
| Secondary Endpoint    | 
 
Change from baseline in the mean home systolic and diastolic blood pressure
 
Change in urinary albumin to creatinine ratio
 
Change from baseline in plasma and urine nitrate, NO metabolites, and ADMA levels
 
  |
| Planned Sample Size   | A total of 60 treated hypertensive participants (1:1; male and female; aged 18-70 years old) with ADPKD (as per the inclusion/exclusion criteria) will be randomised.  |
| Inclusion Criteria    | 
 
Diagnosis of ADPKD
 
Age over 18 years old
 
eGFR > 30 mL/min/1.73m^2
 
Treatment with at least one anti-hypertensive
 
  |
| Exclusion Criteria    | 
 
Inability to provide Informed Consent
 
Labile, unstable uncontrolled hypertension and/or changes in blood pressure treatment in the last 28 days prior to the screening visit that in the opinion of the investigators would confound interpretation of the primary endpoint
 
Non-compliance with daily BP measurements during the screening period
 
  |

|                                       |   |
|---------------------------------------|---|
|                                       | 
 
Medical conditions or treatments that may interfere with the generation of NO metabolites (such as regular use nitrate drugs, cigarette smoking; unwilling to stop using antiseptic mouthwash; uncontrolled severe hypercholesterolemia)
 
Any serious or other medical conditions that may interfere with follow-up or stability of blood pressure (such as current active malignancies requiring treatment; uncontrolled Diabetes Mellitus (elevated HbA1c > 10%)
 
Dislike of taste of beetroot juice
 
Allergy to beetroot
 
Patients enrolled in other clinical trials
 
Pregnant or Lactating
 
   |
| Study Procedures                      | 
 
Clinic and home blood pressure measurement
 
Collection of blood for serum creatinine, eGFR, NO biomarkers and ADMA levels
 
Collection of urine for albuminuria and NO metabolites
 
Collection of saliva samples for genomic analysis of oral bacteria
 
   |
| Samples size and statistical analysis | 
In a previous study of daily BRJ (400mg nitrate) supplementation in hypertensive patients (n=68) for 4 weeks, systolic BP was significantly reduced by 7.7mmHg (3.6-11.8 mmHg, <math>p<0.001</math>) at the end of the intervention. The average BP of the two groups were 148 mmHg and 149 mmHg, with standard deviations of the two populations being 10 and 11.[1] We expected to have a similar hypertensive population and to detect this difference in systolic BP with an <math>\alpha=0.05</math>, and power of 0.80 requires a sample size of n=28 in each treatment group, and to account for drop-out, the group size was therefore increased to 30 (total n=60).
 
The pre-specified research aim was to determine whether once-daily administration of dietary nitrate lowered blood pressure in participants with ADPKD. The pre-specified co-primary endpoints are the change in mean of second and third systolic and diastolic BP measurements taken at Visit 1 (pre-intervention) and at Visit 3 (at the end of week 4 of the intervention). Initially, sample mean and standard deviation will be reported at baseline and follow up. Moreover, their mean difference and standard deviation will be reported. Secondly, the main analysis will be conducted using a Gaussian linear mixed effects (LME) model with a first-order autoregressive correlation structure (AR(1)). The repeated measures are the BP results at Visit 1 and Visit 3. An interaction parameter between Visit and Arm of study will be the determinant of a significant difference in BP change between the two arms. The model will be adjusted for the following prognostic factors: age, eGFR and baseline serum nitrate/nitrite levels. The sensitivity analysis will only be adjusted for age and eGFR. Should any variables differ significantly between the two arms, they too will be adjusted for to eliminate the possibility of a confounding effect. No subgroup analyses will be undertaken. All data analysis will be completed in R version 3.6.2 (R Core Team). All (potential) confounding variables will be summarised using t-tests or rank sum tests for continuous variables and chi-squared tests or Fisher's exact tests for categorical variables. Means (standard deviations) and counts (column percentages) as well as relevant p-values will be reported. Hypotheses will be conducted with a two-sided alternative and p-values less than 0.05 will be considered statistically significant.
 
The secondary endpoint of home BP readings is a set of (at most) 28 daily systolic and diastolic BP measurements averaged from daily home readings. Again, a Gaussian LME model with an AR(1) correlation structure will be utilised. The repeated measures are the BP results at each available home reading. An interaction parameter between Day and Arm of study will be the determinant of a significant difference in the BP change between the two arms. The model will be adjusted for the prognostic variables of age, eGFR and baseline nitrate/nitrite levels as described above. The
 |

|                             |   |
|-----------------------------|---|
|                             | secondary endpoints of change in NO metabolites, serum ADMA and albumin to creatinine ratio will have their differences summarised with sample means, standard deviations, sample mean differences, and sample standard deviations of differences. They too will undergo assessment with a Gaussian LME model as above. |
| Total duration of the study | 35 days (5 weeks) including 7 day run-in period and 28 day intervention period  |
| Timeline                    | Study activity commenced in May 2022 and will conclude in April 2023.   |

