## 2.4 Study Design

[figure not shown]
The total duration of the study is 35 days. Patients will be screened at Visit 1 and eligible patients will be provided with a blood pressure monitor (oscillometric BP device: UA-651, A&D Medical, Tokyo, Japan) to commence baseline home blood pressure monitoring for a 7 day run-in. Their compliance to daily blood pressure readings will be assessed via automated text message each morning (to which participants will reply with their readings), or with a phone call by study staff on Day 2 and 5 if they opt-out of text messages, and at Visit 2. Replying via text message will be encouraged as the preferred option as it will allow for real-time monitoring and data recording and allow patients to easily contact the study team if they have any issues. Participants will be randomly allocated nitrate-rich BRJ (400mg nitrate) or nitrate depleted BRJ (placebo) in a sealed bag and asked not to open it until instructed to do so after Visit 2.

At Visit 2 (conducted via phone), participants' home blood pressure records will be reviewed for compliance. Participants who have recorded  $<80\%$  of the daily blood pressure readings will be deemed non-compliant and excluded from the trial. Additional exclusion criteria assessed at Visit 2 includes eGFR, fasting lipid and glucose levels, use of antiseptic mouthwash (from V1 to V2 and willingness to comply for remainder of study). Any excluded participants will be asked to return all study equipment and the sealed bag of BRJ. Participants who meet all criteria will be asked to commence the intervention that they were allocated the following morning.

The intervention is BRJ commercially packaged BRJ in 70ml bottles. Participants will be instructed to drink one bottle per day (70ml) and measure their blood pressure at the same time every day. Participants will be asked to send their blood pressures via text or record it in their diary. A daily reminder text message will be sent, unless participants opt-out of this option.

After 28 days, participants will return for Visit 3 for post-treatment assessment and sample collection.

Blood and urine samples will be collected at Visit 1 and 3 for measurement of NO metabolites, ADMA levels and urinary albumin to creatinine ratio. A saliva sample will be collected at Visit 1 and 3 for future genomic analysis of oral bacteria.

**Figure 2.** Study design and participant timeline

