### 2.6.2 Statistical and Analytical Plans

#### *Primary Endpoint Analysis*

The co-primary endpoints are the change in mean of second and third systolic and diastolic BP measurements taken at Visit 1 (pre-intervention) and at Visit 3 (at the end of week 4 of the intervention). Initially, sample mean and standard deviation will be reported at baseline and follow up. Moreover, their mean difference and standard deviation will be reported. Secondly, the main analysis will be conducted using a Gaussian linear mixed effects (LME) model with a first-order autoregressive correlation structure (AR(1)). The repeated measures are the BP results at Visit 1 and Visit 3. An interaction parameter between Visit and Arm of study will be the determinant of a significant difference in BP change between the two arms. The model will be adjusted for the following prognostic factors: age, eGFR and baseline serum nitrate/nitrite levels. The sensitivity analysis will only be adjusted for age and eGFR. Should any variables differ significantly between the two arms, they too will be adjusted for to eliminate the possibility of a confounding effect. No subgroup analyses will be undertaken. All data analysis will be completed in R version 3.6.2 (R Core Team). All (potential) confounding variables will be summarised using t-tests or rank sum tests for continuous variables and chi-squared tests or Fisher's exact tests for categorical variables. Means (standard deviations) and counts (column percentages) as well as relevant p-values will be reported. Hypotheses will be conducted with a two-sided alternative and p-values less than 0.05 will be considered statistically significant.

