#### *Secondary Endpoint Analysis*

The secondary endpoint of home BP readings is a set of (at most) 28 daily systolic and diastolic BP measurements averaged from daily home readings. Again, a Gaussian LME model with an AR(1) correlation structure will be utilised. The repeated measures are the BP results at each available home reading. An interaction parameter between Day and Arm of study will be the determinant of a significant difference in the BP change between the two arms. The model will be adjusted for the prognostic variables of age, eGFR and

baseline nitrate/nitrite levels as described above. The secondary endpoints of change in NO metabolites, serum ADMA and albumin to creatinine ratio will have their differences summarised with sample means, standard deviations, sample mean differences, and sample standard deviations of differences. They too will undergo assessment with a Gaussian LME model as above.

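### The run-in home BP is meant to supply a baseline but no specified model names it; the home BP endpoint is therefore tested as a slope rather than as change from baseline, and the clinic BP analysis forgoes usable precision

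*Combined protocol and SAP*

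**What the plan says.** **Purpose of the run-in.** In the Summary (Study Design), participants are "asked to record BP daily to determine adherence and baseline blood pressures". Section 2.4 gives them a monitor "to commence baseline home blood pressure monitoring for a 7 day run-in". The use spelled out there is a compliance rule at Visit 2: participants with under 80% "of the daily blood pressure readings will be deemed non-compliant and excluded from the trial".

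**Clinic BP (co-primary).** Section 2.6.2 defines the endpoints as the "change in mean of second and third systolic and diastolic BP measurements taken at Visit 1 (pre-intervention) and at Visit 3". On the model: "The repeated measures are the BP results at Visit 1 and Visit 3". On the test: "An interaction parameter between Visit and Arm of study will be the determinant of a significant difference in BP change". On covariates: "The model will be adjusted for the following prognostic factors: age, eGFR and baseline serum nitrate/nitrite levels". Any variable that differs significantly between arms is added. No home BP term is named. Visit 2 is by telephone, and Appendix A marks clinic BP only at the first and last visits, so the clinic baseline is one session.

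**Home BP (secondary).** The Summary and Section 2.2.2 define this endpoint as change from baseline. In Section 2.6.2 the analysed outcome "is a set of (at most) 28 daily systolic and diastolic BP measurements", modelled with AR(1) errors. An interaction of Day with Arm decides significance, and no baseline home BP term is listed.

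**The concern.** The trial collects about a week of home readings before treatment, with the same device model, in triplicate, averaging readings 2 and 3 as in the clinic (Section 2.12.1). Two things follow if the models are run as written.

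First, the home BP analysis does not estimate the endpoint it is attached to. Its data begin after treatment starts, so nothing in the model represents the pre-treatment level. The parameter tested is the difference between arms in daily trend. A juice effect that appears in the first days and then holds could be real, useful and missed.

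Second, the clinic BP comparison uses a baseline from one session a week before dosing, in a model that treats that baseline as an outcome. A multi-day pre-treatment mean probably carries further information about Visit 3 BP. In a 60-participant trial that is worth having, provided it is entered in a form that can reach the tested parameter.

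**Working it through.** **1. Home BP: what Day x Arm tests.** Write the treatment effect on day d of treatment (d = 1 to 28) as a + b·d.
- The Day x Arm parameter estimates b alone.
- The mean effect over treatment, relative to a pre-treatment baseline, is a + 14.5·b, since (1 + 28)/2 = 14.5.
- Constant effect, a = 5 mmHg and b = 0 (illustrative): mean effect 5 mmHg, tested parameter 0. The test rejects at about its 5% error rate, whatever the sample size.
- Entering Day as a factor does not help. Interactions measured against the first treatment day are also zero for a constant effect.
- The Arm main effect would absorb a, but the plan does not make it the test, and without the run-in it cannot be separated from chance imbalance at baseline.

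**2. Clinic BP: the plan's own sample size.** Inputs from Section 2.6.1: difference 7.7 mmHg, SDs 10 and 11, power 0.80, alpha 0.05 (two-sided per Section 2.6.2). Formula: n per arm = 2·SD²·(1.96 + 0.84)²/7.7².
- SD 10: 26.5, so 27; a t-test gives 27.47, so 28. The stated 28 reproduces.
- Root-mean-square SD √((100 + 121)/2) = 10.51: 29.3, so 30; a t-test gives 31.

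**3. Clinic BP: what the planned model delivers.** With complete data at two visits, Visit x Arm equals the between-arm difference in mean change. Take equal variances at both visits and let ρ be the Visit 1–Visit 3 correlation. Variances relative to that of a single clinic value:
- planned change contrast: 2(1 − ρ)
- ANCOVA of Visit 3 on Visit 1: 1 − ρ²
- ANCOVA adding the run-in home mean: 1 − R², where R² = (ρ² + r² − 2·ρ·r·q)/(1 − q²), r is the home–Visit 3 correlation and q the home–Visit 1 correlation.

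The documents give none of these correlations. **Assumed:** ρ = 0.5, r = 0.4–0.6, q = 0.5–0.7. The planned contrast is then 2(0.5) = 1.00 and ANCOVA on Visit 1 is 0.75, a 25% reduction.

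| r | q | 1 − R² | Cut vs planned contrast | Further cut vs 0.75 |
|---|---|---|---|---|
| 0.4 | 0.7 | 0.745 | 25% | 1% |
| 0.5 | 0.6 | 0.688 | 31% | 8% |
| 0.6 | 0.5 | 0.587 | 41% | 22% |

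The first and last rows are the extremes of the grid. Middle row: (0.25 + 0.25 − 0.30)/(1 − 0.36) = 0.3125, and 1 − 0.3125 = 0.6875.

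Normal-approximation power with 28 per arm and SD 10.51 is 78.3% for the planned contrast, 88.6% for ANCOVA on Visit 1, and 88.8–94.7% with the home mean added (91.1% in the middle row).

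**4. How the home mean is entered matters.**
- As a main effect common to both visits it cancels from the change. In a simulated two-visit data set the interaction was −7.1085 with and without it.
- As a home-by-visit term in the planned model, the residual variance of change is 2(1 − ρ) − (r − q)². Over the same grid the gain is 0% to (0.4 − 0.7)² = 9%, and 1% in the middle row.

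**5. Sensitivity to ρ.** ANCOVA on Visit 1 relative to the change contrast is (1 − ρ²)/(2(1 − ρ)) = (1 + ρ)/2. The gain from ANCOVA is therefore 25% at ρ = 0.5, 20% at 0.6 and 15% at 0.7.

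**The case against.** **The clinic endpoint is entitled to a clinic baseline.** Home BP is a different measure, the clinic averaging rule follows cited guidelines, and choosing age, eGFR and nitrate/nitrite as covariates is legitimate. This stands. A reader might infer that a single-session baseline biases or invalidates the primary comparison; the documents do not support that. The contrast is randomised, and only precision is at issue.

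**The precision gain is mostly not the home readings' doing.** This also stands. Most of it comes from treating Visit 1 BP as a covariate instead of an outcome. It is tempting to say that the plan throws away free precision, but within the model as specified the home mean gains nothing as a main effect and 0–9% as a home-by-visit term. The lower end of its added value under ANCOVA is about 1%.

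**The readings are used.** They drive the 80% rule, the home endpoint's definition implies them, and the imbalance rule could bring them in. So the inference that the run-in enters no analysis at all goes too far; the accurate statement is that no specified model names it. The imbalance rule is no substitute: it depends on a significance test, and a main effect would not move Visit x Arm.

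**A slope test may suit the biology.** Section 2.7.2 cites a trial in which the home BP effect grew over 4 weeks. But the same section says that the reduction lasted throughout the 4 weeks, and Section 1.1.4 cites an effect within 4 hours. A test blind to the constant part is hard to defend on that evidence.

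**Randomisation at Visit 1 precedes the run-in.** The juice stays sealed and blinded until after Visit 2, so the run-in mean remains a pre-treatment measurement.

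**Conclusion.** The point holds on two levels.

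For home BP it is a mismatch between endpoint and analysis. The endpoint is change from baseline, while the data set and the test described contain no baseline. This conclusion needs no assumed correlations. It rests on reading the 28 values as the 28 treatment days, which their number and the Day x Arm term support, and the blind spot for a constant effect follows directly.

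For clinic BP it is an efficiency point, not an error. Under the assumed correlations the recommended analysis lowers variance by 25–41% against the planned contrast. Of this, 25 points are due to ANCOVA on Visit 1; the home mean cuts the remaining variance by 1–22%. A higher Visit 1–Visit 3 correlation shrinks the ANCOVA share, to 15% at 0.7.

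**What to change.** **Home BP.** Define the home baseline as the run-in mean of the daily averages of readings 2 and 3, and state which run-in days count. Adjust for that baseline. Make the tested parameter the between-arm difference in on-treatment home BP relative to it, either overall or over a pre-specified window such as week 4.

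**Clinic BP.** For each co-primary component, analyse Visit 3 clinic BP by ANCOVA, or by a constrained-baseline model. Pre-specify Visit 1 clinic BP and the run-in home mean of the same component as covariates, alongside those already listed. Do not enter the home mean as a main effect common to both visits in the current model, since that leaves Visit x Arm unchanged.

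**Cost.** The wording and the tested parameter of both the primary and the home BP models change in the Summary and Section 2.6.2, which is more than an added covariate and should be settled before unblinding. The home covariate uses one degree of freedom. No new visits, measurements or participants are needed, and the 80% compliance rule means that few participants should lack a run-in mean.

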## 2.6 Statistical Methods

### 2.6.1 Determination of Sample size

In a previous study of daily BRJ (400mg nitrate) supplementation in hypertensive patients (n=68) for 4 weeks, systolic BP was significantly reduced by 7.7mmHg (3.6-11.8 mmHg,  $p<0.001$ ) at the end of the intervention. The average BP of the two groups were 148 mmHg and 149 mmHg, with standard deviations of the two populations being 10 and 11.[1] We expected to have a similar hypertensive population and to detect this difference in systolic BP with an  $\alpha=0.05$  and power of 0.80, 28 participants are required in the each treatment group. To account for drop-out, the sample size was increased to 30 participants per treatment group (total n=60).

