#### **2.8.2 Randomisation**

Eligible participants will be randomised 1:1 at Visit 1 to receive either dietary nitrate or placebo using a simple randomisation program created by the study biostatistician, which uses a random number generator (version 3.6.2, R Core Team). This program creates a list that allocates treatment or placebo (1:1) to 60 unique study IDs. No stratification factors will be used. Participants will not consume the intervention until instructed to by trial staff at Visit 2.

If a participant is deemed ineligible between Visit 1 and 2, they will be asked to return the sealed beetroot juice given to them to the trial staff. The AI who is responsible for blinding will reallocate the BRJ as per the randomised number list created by the statistician.

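### Blood nitrate/nitrite: read literally, the plan makes the Visit 1 value both a covariate and an outcome row, which is harmless or anti-conservative depending on a covariance choice left unstated

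*Combined protocol and SAP*

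**What the plan says.** Section 2.6.2 (Primary Endpoint Analysis) and the matching Summary row define a Gaussian mixed model with an AR(1) correlation. Visit 1 and Visit 3 values are both outcomes, the Visit by Arm interaction is the test, and the covariates are age, eGFR and baseline serum nitrate/nitrite. A sensitivity analysis without the nitrate/nitrite covariate is described there for the primary endpoints. On testing: "Hypotheses will be conducted with a two-sided alternative", and "p-values less than 0.05 will be considered statistically significant".

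For home blood pressure the covariates are restated: "The model will be adjusted for the prognostic variables of age, eGFR and baseline nitrate/nitrite levels as described above". For NO metabolites, ADMA and albumin to creatinine ratio the plan gives descriptive summaries and then one sentence: "They too will undergo assessment with a Gaussian LME model as above". No covariate is dropped or replaced for any of these endpoints.

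Section 2.12.2 takes serum at Visits 1 and 3 for the nitrate/nitrite measurement, and section 2.13.1 describes one Griess-based assay for it. The endpoint lists call the measurement plasma, but 2.12.2 provides for a single serum tube. The baseline covariate and the Visit 1 endpoint value are thus the same measurement.

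**The concern.** Whichever main model is meant by the cross-reference, primary or home blood pressure, baseline nitrate/nitrite is among its covariates. When the outcome is blood nitrate/nitrite, the Visit 1 row is then regressed on itself (true slope 1) and the Visit 3 row on Visit 1 (true slope r, the between-visit correlation under equal variances), with one shared coefficient. No single value fits both rows, and the misfit passes into the residual covariance.

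At stake is the standard error of Visit by Arm for one named secondary endpoint. Whether it is right depends on whether the fitted covariance can be negative. The plan names AR(1) but does not state the random effects. With two visits and a common residual variance, a random intercept variance, a residual variance and an AR(1) parameter are three quantities fitted to one variance and one covariance, so they are not separately identifiable. An analyst may have to drop one, and the plan does not say which.

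**Working it through.** **Inputs from the documents.** Two-sided alpha 0.05. Allocation: "Eligible participants will be randomised 1:1 at Visit 1". Size: "power of 0.80, 28 participants are required in the each treatment group", raised to 30 for drop-out.

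**Assumed, because the documents are silent.** SD 1 at both visits, Visit 1 to Visit 3 correlation r from 0 to 0.8, no treatment effect; unequal variances are examined in step 5.

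**The plan's own figure.** It concerns systolic pressure only and serves here just to set n. The inputs are "systolic BP was significantly reduced by 7.7mmHg" and "standard deviations of the two populations being 10 and 11". With n = 2(1.960 + 0.842)² SD²/7.7²:
- SD 10: 26.5, so 27 (28 by the t distribution)
- SD 10.5: 29.2, so 30 (31 by t)
- SD 11: 32.0, so 33 (34 by t)

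So 28 is reproduced with SD 10. No size is stated for nitrate/nitrite.

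**Step 1, slope.** The covariate is constant within a person, so with complete data its coefficient comes from the person sums: 2b = Cov(y1 + y3, y1) = 1 + r, hence b = (1 + r)/2.

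**Step 2, residuals.** e1 = y1(1 − r)/2 and e3 = y3 − b·y1.
- Cov(e1, e3) = −((1 − r)/2)²
- mean of the two residual variances = (1 − r)(3 + r)/4
- implied correlation = (r − 1)/(3 + r), negative for every r below 1

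**Step 3, standard error of Visit by Arm.** The true variance of a within-person change is 2(1 − r).
- Correlation free in sign: the fit recovers 2(1 − r), the change-score variance, with or without the covariate. In one simulated dataset at r = 0.3 the SE was 0.3585 both ways and the estimate 0.2859 both ways.
- Correlation floored at zero: the fit uses (1 − r)(3 + r)/2, so the SE is multiplied by √((3 + r)/4), which is 0.866 at r = 0 and 0.949 at r = 0.6 (13% and 5% too small). Large-sample type I error is 2[1 − Φ(1.96 × 0.866)] = 9.0% and 2[1 − Φ(1.96 × 0.949)] = 6.3%. In the same dataset the SE fell to 0.3212.

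**Step 4, simulation.** 28 per arm, 20,000 null trials per row, complete data. The Monte Carlo error of a 5% rate is √(0.05 × 0.95/20,000) = 0.15 points.

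| r | Implied correlation | SE, free AR(1) | SE, correlation ≥ 0 | SE, ANCOVA | Type I, free | Type I, ≥ 0 | Type I, ANCOVA |
|---|---|---|---|---|---|---|---|
| 0 | −0.333 | 0.3761 | 0.3277 | 0.2741 | 5.03% | 8.55% | 4.72% |
| 0.2 | −0.250 | 0.3368 | 0.3025 | 0.2682 | 4.86% | 7.63% | 5.03% |
| 0.3 | −0.212 | 0.3148 | 0.2870 | 0.2610 | 4.78% | 7.07% | 4.76% |
| 0.5 | −0.143 | 0.2659 | 0.2494 | 0.2371 | 5.12% | 6.54% | 5.08% |
| 0.7 | −0.081 | 0.2062 | 0.1985 | 0.1956 | 4.96% | 5.77% | 4.92% |
| 0.8 | −0.053 | 0.1683 | 0.1641 | 0.1643 | 4.94% | 5.55% | 4.93% |

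The ratio of change-score to ANCOVA SE is √(2/(1 + r)) in theory: 1.41 at r = 0 and 1.12 at r = 0.6. The simulated ratio at r = 0 is 0.3761/0.2741 = 1.37.

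**Step 5, departures from these assumptions.**
- Unequal variance (30 per arm, r = 0.3): with the active-arm Visit 3 variance 4 or 9 times larger, the floored fit gives type I error of 5.8% or 5.6%. The change-score and ANCOVA SEs are then 0.414 and 0.399 (4 times), or 0.562 and 0.566 (9 times).
- Missing data (2 of 30 per arm missing at random, 800 runs, r = 0.3 and 0.5): type I error is 5.0% and 6.3% with free AR(1), 7.1% and 8.4% when floored. Monte Carlo error here is about √(0.05 × 0.95/800) = 0.8 points, so the free-AR(1) results are compatible with 5%.

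**The case against.** The strongest reply is that the plan names an AR(1) structure, not a random intercept alone, and an AR(1) parameter may be negative. With that model and complete data the test is valid. This stands: inflated type I error is a risk of one implementation, not a property of the plan as written.

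Second, the cross-reference is loose. The covariates are introduced as prognostic factors for blood pressure, are restated for home pressure, and are not restated for the biomarkers. The authors may never have meant to carry this one over. That is possible, but no exception is written, and the analysis without the covariate is described only for the primary endpoints.

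Third, equal variance is an unfavourable assumption here. One arm takes 0.4 g nitrate daily and the other none (Table 2), so active-arm variance may well rise, and step 5 shows that both effects then nearly vanish. This also stands, and limits how much weight the sizes can bear.

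Fourth, the shared coefficient is uninterpretable, but the plan bases inference on the interaction and does not propose to report that coefficient. I therefore place no weight on it.

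A reader might also infer that the duplicated covariate makes the test needlessly imprecise. It does not: with complete data and free AR(1) the standard error is identical without it. The gap to ANCOVA comes from testing Visit by Arm with Visit 1 as an unconstrained outcome, which the blood pressure models do too.

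**Conclusion.** The model is mis-specified as written for blood nitrate/nitrite, and only for that endpoint. Blood pressure, ADMA, albumin to creatinine ratio and urine NO metabolites do not have their own baseline as a covariate. The complete-data estimate of the interaction is unaffected.

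With AR(1) kept and free in sign, type I error is about 5% and the covariate is inert. With a fit that cannot be negative, the standard error is about 5-13% too small and type I error about 6-9%, for r from 0 to 0.6 and equal variances. The ANCOVA gain of roughly 10-40% in standard error over the same range is a separate matter. Inflation and gain both shrink as r rises and nearly disappear if active-arm Visit 3 variance is 4-9 times larger. Since r and the SDs are not in the documents, these are ranges under assumption, not predictions.

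It is tempting to conclude that the planned test must have an error rate above 5%. The documents do not support that, because the structure they name can absorb the negative correlation. What they support is that validity rests on a covariance choice the plan leaves open.

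**What to change.** In the Summary and section 2.6.2, state that blood nitrate/nitrite is analysed as the Visit 3 value on arm, with the Visit 1 value, age and eGFR as covariates (ANCOVA), so that Visit 1 is used once. If both visits are to stay as outcome rows, remove baseline nitrate/nitrite from the covariates of that model and constrain the arms to a common Visit 1 mean. Removing the covariate alone cures the understated standard error but gives no gain in precision. Listing the covariates for each secondary endpoint would also settle the cross-reference.

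The cost is one sentence of analysis-plan wording, with no new data and no change in sample size. The downside of ANCOVA is that participants without a Visit 3 sample do not contribute to it.
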